## 10. HUMAN SUBJECTS

Subject Population: We seek to recruit 30 REC AN, 30 REC AN-BN, 30 REC BN, and 30 CW, between ages 18 to 45 for the PET imaging studies. It is our experience from previous studies that it will be necessary to enroll an additional 20% of subjects due to drug failure, non-completion of PET studies, etc. Thus, we expect to complete PET studies in a total of 100 subjects (25 REC AN, 25 REC AN-BN, 25 REC BN, and 25 CW).

Only right-handed subjects will be included as screened by the Edinburgh Handedness Inventory. The rationale for including only female subjects is that AN, AN-BN and BN among males is relatively rare (less than 10% in our experience). Furthermore, because some males with AN, AN-BN or BN have many atypical features, they should be subjects of a different study. All subjects will be matched by age, IQ, income, race/ethnicity, and will be non-smokers. REC AN, REC AN-BN, REC BN, and CW will be matched by BMI. Subjects will be recruited locally and nationally to reflect the racial/ethnic composition of the United States, which encompasses a wide range of ethnically diverse individuals (i.e., 65.6% White persons, not Hispanic, 15.4% Hispanic or Latino origin, 0.2% Native Hawaiian and Other Pacific Islander, 4.5% Asian persons, 1.0% American Indian and Alaska Native persons, 12.8% Black persons, 79.8% White persons (<http://quickfacts.census.gov/qfd/states/00000.html>)). While every effort will be made to recruit participants in respective proportion to these demographics, it has been our experience that patients with AN, AN-BN and BN tend to be predominantly white. Subjects fulfilling all the inclusion, but none of the exclusion criteria, will be admitted to the study. No exclusion criteria shall be based on race or ethnicity.

Inclusion Criteria for REC AN, REC AN-BN and REC BN Women: REC AN, AN-BN and BN subjects must have, at some point in their life, met a DSM-IV diagnosis of AN and/or BN. The onset of their illness must have been at least 4 years prior to participating in this study. Due to the high rate of conversion from AN to BN within 3 years of onset, this time requirement will ensure that they did not convert from one diagnostic subtype to another. Thus, diagnostically “pure” groups may be obtained. REC AN women must have met DSM-IV criteria for AN, restricting type, with an ABW below 85% for height. They must never have engaged in binge eating (as defined in DSM-IV) or purging behaviors (e.g., vomiting, laxative or diuretic abuse, enemas, etc.). REC AN-BN subjects must, at some point in their life, have been below 85% ABW and have had bingeing/purging behaviors during a period of low weight. REC BN must have met a lifetime DSM-IV diagnosis of BN with no history of AN. They must have engaged in binge eating (as defined in DSM-IV) followed by vomiting at least once a day for 3 days of the week over at least a 3-month period. All subjects must be right-handed.

ED groups must have been REC for 12 months or more prior to entering the study. Status of recovery will be

defined as follows: a) No bingeing, purging, restrictive eating or other ED related behaviors in the preceding 12 months; b) Maintained a stable weight ( $\pm 3.0$  kg) between 90% and 120% ABW for at least 12 months; c) Regular menstrual cycles for the preceding 12 months; d) Have values within the normal range for beta-hydroxy-butyric-acid (BHBA), glucose, and insulin during the evaluation phase. Subjects will be studied during the first 10 days of the menstrual cycle (early follicular phase).

Exclusion Criteria for REC AN, REC AN-BN and REC BN Women: a) Met diagnosis of alcohol or drug abuse or dependence in the 3 months prior to the study. Alcohol or substance use within 30 days prior to PET studies as determined by self-report, clinical or psychiatric interviews, or urine toxicology screen; b) Current diagnosis of an Axis I major affective or anxiety disorder or suicidal thoughts, or presence of other psychopathology that might interfere with ability to participate in the study, (e.g., requiring inpatient hospitalization or medication); c) Organic brain syndromes, dementia, psychotic disorders, or mental retardation; d) Neurological or medical disorders such as seizure disorder, renal disease including pyelonephritis and chronic cystitis, impaired renal function including hyponatremia (less than 135 meq/l), hypokalemia, raised BUN (more than 15 mg/dl), raised creatinine (more than 1.5 mg/dl), diabetes, thyroid disease including hyperthyroidism and hypothyroidism, EKG indicative of electrolyte imbalance; e) BN subjects whose primary or only purging methods were the use of laxatives, diuretics or means other than vomiting; f) Use of psychoactive medication in the 3 months prior to the study; g) Pregnancy, lactation or lack of effective birth control during the 15 days before the scans. A pregnancy test will be conducted within 24 hours of the study; h) Tobacco use in the 3 months prior to the PET studies.

Criteria for CW: Healthy CW must not have any stigmata suggestive of an ED. They must have maintained an ABW between 90% and 120% since menarche. Their lab tests, medical and psychiatric histories, and physical and neurological examinations should indicate no current or past psychiatric (definitive Axis I disorder), medical or neurological illness. We recognize that these criteria will create a selection of healthier than average control subjects. However, it was deemed more important to avoid the potentially confounding effects of psychiatric symptomatology in the control group with regard to the biological measures for the current study. All pregnant and lactating women will be excluded.

## 11. RECRUITMENT

This is a five-year study in which we will recruit equal numbers of subjects each year. It is our experience from previous studies that it will be necessary to enroll an additional 20% of subjects due to drug failure, non-completion of PET studies, etc. Thus, we expect to enter 30 subjects to complete cells of 25 radioligand/PET studies per subject group. Overall, we will enter 120 subjects into this study in 5 years or 24 subjects per year.

Since at least 50 to 70% of individuals who have anorexia or bulimia eventually recover, we are confident that our recruitment goal can be achieved over the proposed 5-year period. All CW will be recruited from the greater San Diego region to minimize travel cost. However, based on our experience, approximately 75% of our REC subjects will come from outside southern California.

We will continue to employ recruitment strategies that were effective in our previous studies. These include: a) mailings to former patients of UCSD and the University of Pittsburgh ED treatment programs and other nationally recognized ED treatment programs directed by colleagues; b) mailings of IRB approved flyers to clinicians and treatment centers specialized in EDs, and to university health and counseling centers; c) placing advertisements and study announcements in ED related publications, press releases and conferences (e.g., NEDA, AED and EDRS); d) placing study advertisements on websites such as EDReferral and NEDA. We will also utilize the UCSD research websites which make available to professionals and the lay public alike our research publications and current findings; e) We may also contact participants who have been in our previous studies and who appear to be appropriate potential participants for this current study, provided they have given written permission to recontact them. There will be no cold-calling to any potential participant.

Subjects will contact our staff by either phone or email at which time we will ask initial screening questions which do not contain any identifiable information: age, weight, height, use of medications, handedness and presence of metal in the body. Our procedure is to establish if prospective study participants meet minimal criteria as described before proceeding to explain the protocol and obtain address to send out consent form and self-report questionnaires. If subjects are disqualified at this time their information will be destroyed. If preliminary requirements are met, this information is destroyed (page 1 of brief screening tool) and we would then proceed to obtain mailing information. This information is the same as would be asked if the subject was being set up for a clinical appointment. The only information retained will be name and address, and phone number. The protocol will then be explained to the subject and we will then mail a consent form and self-assessment questionnaires to the subject. If a subject declines to participate or does not meet the minimal required inclusion criteria as per brief screening tool, the information obtained will be destroyed. This information will also be destroyed after receiving a signed consent form back from a subject or in the case of no response after sending the consent information to a subject.

Recruitment will be accomplished by posting IRB approved flyers, website ads, craigslist, The San Diego Reader and ads in local and regional publications. Potential subjects can respond to these advertisements by phone or in writing. Many potential participants will live outside the immediate San Diego area; these potential research subjects would probably be unwilling to participate if they were required to come to UCSD to sign a written consent and undergo the initial screening. Also, because many subjects are excluded before completing the entire initial screening, requiring a trip to UCSD for a preliminary screening would be very time and cost intensive and therefore delay the completion of the study. Therefore, these subjects approaching us about participating in research will undergo a brief interview or telephone screening conducted by our research staff. This screening is designed to give a preliminary indication of whether or not the subject will be appropriate for this research study based upon current age, height, weight, and if the subject is currently on any medications. The preliminary screening tool is enclosed. It contains no name or identifier, (page 1). The only information retained will be name and address, (page 2). Written consents will then be obtained from the participant before any information is obtained for the in-depth screening process. If potential subjects appear to meet inclusion criteria (age, weight, height, and absence of medications) the research program will be explained to the subjects. All information is confidential and would not affect an individual's employability or reputation.

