In **Aim 2A**, we propose to use PET and [C]raclopride binding to confirm several hypotheses generated by our preliminary data regarding striatal DA D2/D3 receptors. First, that REC AN, and perhaps REC BN, have elevated anterior ventral striatum (AVS) [C]raclopride (DA D2/D3 receptor) BPND compared to CW. Second, that dorsal caudate (DC) [C]raclopride BPND in REC eating disorders (EDs) is associated with baseline harm avoidance (HA), a measure of inhibition and anxiety.

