In **AIM 2B**, we will assess endogenous striatal DA release in order to better understand altered striatal [C]raclopride binding, and (in **AIM 2C**) to replicate and extend pilot data that show that endogenous DA release in the dorsal caudate (DC) provokes inhibitory and anxiety symptoms in AN and BN. In brief, because [C]raclopride binding is influenced by endogenous DA, elevated [C]raclopride binding could indicate either an elevation of the density and/or affinity of the DA D2/D3 receptors or a reduction of intrasynaptic DA concentrations. It has been shown in non-human primate studies that the decrease in the BPND of benzamide radiotracers such as [C]raclopride following amphetamine (AMPH)-induced DA release is a reliable measure of endogenous DA transmission in striatal subdivisions (limbic, associative and sensorimotor striatum). AMPH administration results in an increase in extracellular DA and a consequent reduction in [C]raclopride binding. The change ( $\Delta$ ) in BPND (the difference between the [C]raclopride BPND at baseline and post-AMPH treatment normalized to the baseline BPND and expressed as a percentage) provides a non-invasive measure of changes in DA concentration in the human brain. We will use the PET/double [C]raclopride/AMPH paradigm described above to assess striatal endogenous DA release. Several recent, small scale studies using this technology and a previous study of cerebral spinal fluid (CSF) homovanillic acid (HVA), a DA metabolite, support the likelihood that REC AN and BN have alterations of endogenous striatal DA release. In AIM 2B we will assess endogenous DA release to help interpret alterations in DA functional activity as well as D2/D3 receptors in limbic, associative, and sensorimotor striatal regions. As summarized in **Table 1** we predict that endogenous DA release will be selectively diminished in limbic striatal regions in REC AN and in associative and sensorimotor regions in REC BN. These data argue that AN have diminished ability to direct “motivated” responses whereas BN may have hypoactive dorsal associative inhibitory pathways. Several lines of evidence support our hypothesis that alterations of food-induced DA secretion, perhaps acting on DA D2 receptors, contribute to pathologic eating. In **AIM 2C** we seek to replicate and extend findings that AN have a paradoxical response to palatable foods because endogenous DA release in the DC is anxiogenic in AN. This anxiogenic effect is compensated for by restricted eating to avoid anxiety. We will also test the hypothesis that a measure of altered inhibition in AN is associated with DC DA D2 binding.

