
Behavioral disorders may be caused by complex disturbances in neural pathways. The relationship between altered 5-HT and DA function (and effects on ventral limbic and dorsal cognitive circuits) may modulate pathological feeding behavior in AN and BN. In brief, 5-HT and DA systems are thought to interact (with 5-HT being aversive/inhibitory, and DA modulating reward/motivation) to regulate appetitive processes. Our data

	Limbic DA	Balance	Associative DA
AN	↓	<	N
AN-BN	↓	Dysregulated	↓
BN	N	>	↓

**Table 1** Model of striatal DA functional activity and the balance of limbic versus associative DA striatal circuitry

showed positive correlations between striatal [C]McN5652 BPND and [C]raclopride BPND in REC AN, REC AN-BN, and REC BN. Interactions between [C]McN5652 BPND and [C]raclopride BPND significantly predicted harm avoidance (HA), a measure of inhibition and anxiety, in REC ED. We hypothesize that binding of these ligands may reflect complex 5-HT – DA neurotransmission interaction processes. In **AIM 3** we seek to replicate these findings and determine whether a similar relationship occurs in CW.

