#### Relationship of endogenous DA release to anxiety and/or inhibition in AN and BN:

**Background:** Considerable literature (see ) shows that HA, a multifaceted temperament trait that contains elements of anxiety, inhibition, and inflexibility, is elevated in individuals who are ill with AN and BN and persists after recovery. As noted above, DC [C]raclopride BPND is positively correlated with HA. Importantly, increased DA D2-like receptor functional activity is associated with inhibition in healthy humans. Moreover, rats characterized as risk averse show greater D2 mRNA expression in the DC. In Aim 2C, we seek to explore how DA signaling in associative /executive cortical striatal circuitry may be related to inhibition and/or adverse consequences in AN and BN.

**Anxiety:** The major goal in Aim 2c is to replicate and extend our finding that self-reports of HA are associated with baseline D2 binding in the DC in AN and BN, and self-reports of anxiety are

**Figure 1:** Predicted relationship between SSRT and baseline [C]racloprideBPND. Gray shade, range of individual responses; ●, mean CW values; O, mean AN values at baseline; →, predicted change when post-AMPH SSRT is compared with baseline [C]racloprideBPND.

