**Exposure to high magnetic fields:** All subjects will be screened twice before they will be allowed to enter the MRI facilities. Any non-removable magnetic material will automatically exclude subjects. All staff is regularly trained in MRI safety procedures by the PI.

**Heating from radiofrequency (RF) pulses:** The MRI pulse sequences that will be used are discussed prior to usage by the MR physicists and the director of the Center for Magnetic Resonance Imaging (CMR) with respect to potential heating effects. The physicists at the CMR regularly test pulse sequences on phantom objects for heating effects.

**Acoustic noise:** Subjects will be instructed to wear earplugs or headsets that reduce the noise by about 20-40 dB. Subjects will be instructed to indicate if the noise is a source of physical or psychological discomfort. If this were to occur the experiment will be terminated immediately.

**PET and Radiation related issues** The use of [C] radioligands in this research proposal is considered to be generally safe and effective as approved by the University of California, San Diego Radioactive Drug Research Committee in accordance with Food and Drug Association regulation 21 CFR 361.1. No PET studies will be performed on pregnant or potentially pregnant women, as confirmed by pregnancy testing performed within 24 hours prior to each PET scanning session. The total Occupational Dose Limit / EDE for adults, as regulated by the US Nuclear Regulatory Commission is 5.0 rem per year. Thus, for the three studies the EDE is about 24.64% of the radiation dose (5 rem) permitted on an annual basis to radiation workers by federal regulations (21 Code of Federal Regulations (CFR) 361.1. If an X-ray study is required to rule out the presence of metallic fragments, the maximum radiation dose to the involved body area will be 0.3 rems (a unit of radiation dosage), with minimum exposure of the other areas of the body. In order to restrict the yearly cumulative exposure to

radiation as outlined in FDA 21.361.1, all subjects exposed to radiation in the work place are excluded, as well as subjects exposed to nuclear medicine procedures during the previous year, including research protocols. In case of idiosyncratic reactions to the radiotracers, a physician is present at each experiment and will be available at all times during the study and an emergency cart will be in close proximity.

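### Women from the group's earlier PET studies can be re-enrolled and nothing identifies them, so any who return would count as independent replication in Aims 2A, 2C and 3

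*Combined protocol and SAP*

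**What the plan says.** Section 11 (Recruitment) gives five recruitment routes. The last is recontact: "We may also contact participants who have been in our previous studies and who appear to be appropriate potential participants for this current study". Apart from apparent suitability, the woman's written permission is the only condition.

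The eligibility criteria in Section 10 do not mention earlier participation. Neither do the telephone screening items in Section 11. Section 15 has the only rule on earlier PET. In order to limit yearly radiation dose it excludes people exposed to radiation at work, "as well as subjects exposed to nuclear medicine procedures during the previous year, including research protocols". A woman scanned in an earlier study more than a year ago is not barred by it.

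Three aims in Section 6 rest on the group's own earlier data:
- Aim 2A is "to confirm several hypotheses generated by our preliminary data regarding striatal DA D2/D3 receptors".
- Aim 2C is "to replicate and extend pilot data". Section 7 repeats this: "The major goal in Aim 2c is to replicate and extend our finding that self-reports of HA are associated with baseline D2 binding".
- Aim 3, on the relation between serotonin transporter and D2/D3 binding, says "we seek to replicate these findings and determine whether a similar relationship occurs in CW".

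The Power and Statistical Analysis Plan in Section 9 has no flag for returning women, no restriction to new participants and no sensitivity analysis without them. Section 8 reports 47 women enrolled and does not say whether any took part before.

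**The concern.** A confirmation or replication adds evidence to the extent that its sample is independent of the one that suggested the hypothesis. The protocol treats the monoamine alterations as persistent and trait-related (Section 6) and harm avoidance as persisting after recovery (Section 7). On that premise a woman measured again brings back much of her earlier value, including whatever part of the pilot result was chance. If enough pilot women return, a chance finding becomes more likely to be confirmed than the nominal error rate suggests. A reader of the results could not tell whether overlap was nil or substantial.

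**Working it through.** **Reading the text.** Recontact is allowed (Section 11), the only PET bar is one year (Section 15), no criterion covers prior participation (Section 10), and no analysis separates returning women (Section 9). Followed as written, the plan counts a returning pilot woman as a new, independent observation. This step needs no arithmetic.

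**Size.** The plan gives no figure on this point, so there is none to reproduce. The calculation below is illustrative.

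Inputs from Section 9, Aim 2A: AVS raclopride binding 2.404 (recovered AN) and 2.120 (control women), SD 0.359, n = 25 per group, two-sided 0.05. So d = (2.404 − 2.120)/0.359 = 0.284/0.359 = 0.79.

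Assumptions, not in the documents: the whole pilot difference is chance, a fraction f = 0.1 to 0.4 of each affected group are returning pilot women, and the retest correlation r is 0.7 to 0.9. The plan's only related figure is a pre-post correlation of 0.90 within one day (Aim 2B).

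Formulas:
- Carried-over difference, both groups overlapping: f × r × d.
- Only eating-disorder (ED) women returning, with the chance deviation split equally between the groups: f × r × d / 2.
- Rejection rate: two-sided two-sample t-test, 48 df, noncentrality = difference × √(25/2).

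| f | r | Both groups: difference (SD) | Rejects | ED only: difference (SD) | Rejects |
|---|---|---|---|---|---|
| 0.1 | 0.7 | 0.055 | 5.4% | 0.028 | 5.1% |
| 0.2 | 0.9 | 0.142 | 7.8% | 0.071 | 5.7% |
| 0.4 | 0.9 | 0.285 | 16.7% | 0.142 | 7.8% |

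**Second check, by simulation.** A pure-noise pilot with an assumed 10 women per group is kept if significant at two-sided 0.05 in the predicted direction. The new study (25 per group) is then scored for significance in the same direction, for which the nominal rate is 2.5%. Ranges are for r = 0.7 to 0.9.

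| Returning, of 25 | Mean difference, ED only | Mean difference, both groups | Within-group correlation |
|---|---|---|---|
| 3 | 3.6–3.7% | 4.8–5.5% | 3.9–4.7% |
| 5 | 3.9–4.8% | 6.9–8.4% | 4.7–6.5% |
| 10 | 7.1–8.6% | 14.4–21.6% | 8.0–15.6% |

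With no returning women the simulated rate is 2.2–2.8%. The last column bears on within-ED relationships such as dorsal caudate binding with harm avoidance, which new control women do not protect.

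**The case against.** The strongest reply is that nothing shows any overlap. Recontact is a permission and the last of five routes. The earlier studies it refers to are not limited to the PET pilots, since the group also cites its own CSF, fMRI and personality work. A reader might infer that the sponsor is actively recruiting pilot women, or that some of the 47 have been scanned before. The documents support neither. The age limits, recovery criteria and pre-amphetamine checks also narrow who can return. All of this stands. It limits the likely size and leaves the gap in the plan open.

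A reader might also take 17% as the trial's false-positive rate. That does not follow. The figure needs 40% overlap in both groups, r = 0.9 after more than a year, and a wholly chance pilot difference. Controls come only from greater San Diego, so the ED-only range may be nearer the mark, but the documents do not say where the pilot controls lived. The calculation is also before the Troendle adjustment planned for Aim 2A. It is conditional on a chance pilot result. Unconditionally, the new test keeps its level, so the issue is the independence of the evidence, and the test itself is not faulty.

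The aims are not equally exposed. Aim 3 changes the transporter tracer from [11C]McN5652 to [11C]DASB and asks a new question in controls. The powered test in Aim 2C compares correlations between ED and control groups and adds new outcomes. Returning ED women would still not be a fresh sample for either aim, but the dependence is less direct for Aim 3.

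Finally, removing returning women from the main tests could be costly. At 40% overlap n falls from 25 to 15 per group, and power for d = 0.79 falls from 78% to 55% (same t-test; the plan's own claim of more than 90% is a separate matter). This objection stands and shapes the fix.

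**Conclusion.** The point holds as a gap in the design. The plan allows re-enrolment of women who may have generated its hypotheses, does not identify them, and would count them as independent support for Aims 2A, 2C and 3. Whether overlap exists is unknown. Under the assumptions above, the unadjusted 5% test of the AVS difference would reject in about 5.1–7.8% of trials if only ED women return and about 5.4–17% if both groups overlap. These are conditional illustrations, and at 10% overlap the effect is close to nil. The documents do not support a finding that the replication is already compromised, or a requirement to drop returning women from the main analyses.

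**What to change.** In Sections 10 and 11, record for every woman whether she took part in each of the hypothesis-generating PET studies. Complete this for the 47 already enrolled from the group's own records, and report the number per group.

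In Section 9, keep all women in the main analyses of Aims 2A, 2C and 3. Pre-specify the same analyses without the women who contributed to the earlier data sets, and state that independent replication will be claimed only on the basis of these new-participant results.

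The cost is one screening item, a record check and a short addition to the analysis text. No recruitment route closes and no woman is excluded from the study. The new-participant analysis loses precision if overlap is substantial. If overlap is nil, the two analyses coincide and independence is documented.
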